12.1 Study Schedule

Visit-1 (Procedure Day)	Visit-2 (Follow up)
Informed Consent	Assessment of AE
Screening (Eligibility Criteria)	Study Exit
Demographics and Medical History	
Imaging with VIO (Study Procedure)	
Assessments for AE, PD, DD (if any)	

12.2 Recruitment

Potential subjects will be recruited from the Investigator's practice, referrals, and local advertising. Any study-related advertisements will be approved by the governing IRB prior to use. Consecutive subjects meeting the inclusion and exclusion criteria will be recruited based on the guidelines described above in Tables 1 – 5.

12.3 Informed consent process

All subjects or LARs must be provided a consent form describing the study with sufficient information for subjects to make an informed decision regarding their participation. Subjects or LARs must sign the IRB approved informed consent prior to participation in any study specific procedure. The subject or LAR must receive a copy of the signed and dated consent document. The signed copy of the consent document must be retained in the subject's study file. A patient who is eligible and signs the study consent will be considered a study subject.

12.4 Screening

After the subject or LAR provides written informed consent, the subject will be screened by the Investigator or designee using the protocol defined inclusion and exclusion criteria to determine study eligibility. The subject screening interview will collect demographic data and relevant medical history.

All subjects who are eligible with a signed informed consent form will be assigned a unique screening ID number. Only subjects who undergo device use will count towards the study's sample size.

12.5 Demographics and medical history

Demographic data to be collected will include date of birth, race, ethnicity, and Fitzpatrick skin type. Relevant medical history (i.e., previous diagnoses, diseases, or surgeries) will also be collected.

12.6 Procedure

- a. Study staff will procure images of the planned biopsy site using a standard camera and dermatoscope
- b. Trained device users will procure VIO *in vivo* images:
 - i. at the planned biopsy site
 - ii. at a contralateral (preferred) or nearby non-suspicious site of uninvolved-appearing tissue
- c. Approximately 20-100 images will be taken for each planned biopsy site and 2-10 images will be taken for each uninvolved site. Approximately 4-8 representative images from the planned biopsy site will be selected for further review/assessment.
- d. Physical H&E slides from the biopsy site may be converted into digital pathology images by the Investigator or the Sponsor using a commercially available scanner.
- e. Subjects will be asked to answer a brief questionnaire about their opinions and/or experience

12.7 Follow-Up Phone Call

A phone call follow-up evaluation will be conducted 7 days (+/-3 days) after the study procedure to record adverse events.

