	subjects may be enrolled in the study in order to meet comparable distribution of samples described in the protocol.
Inclusion and Exclusion Criteria	
Inclusion Criteria:
 
 1. The subject is between 18 and 99 years of age. 2. The subject or Legally Authorized Representative (LAR) is able and willing to provide written informed consent. 3. The subject is planning to undergo a routine skin biopsy. 4. The subject is willing and able to remain still for periods of up to 3 minutes to allow for image capture. 5. The subject or LAR has sufficient mental capacity to understand the informed consent form (ICF) and comply with the protocol requirements. 
Exclusion Criteria:
 
 1. The subject has a general health condition or systemic disease that in the opinion of the physician, precludes them from trial participation. 2. The subject has a known allergy or increased skin sensitivity to silicone, adhesives, or glycerin. 3. The subject's lesion targeted for biopsy: 
 a. Is located on the palms of the hands, soles of the feet, fingernails, or toenails. b. Has dense hair that will not be removed prior to the skin biopsy. c. Has clinically significant abraded or ulcerated skin with or without discharge. d. Is associated with a wound or skin condition that in the opinion of the physician precludes them from participation e. Is located in mucosal tissue (i.e., oral, nasal, etc.). f. Is on tattooed skin. g. Is on a skin formation too tortuous for the investigational device to access (e.g., skin tags.) h. Is located in the periorbital region or directly on the eyelid.
Investigational Device	
VIO, the investigational device, is a noninvasive real-time skin imaging device that can provide histology-like images of skin epithelial tissue with subcellular resolution and dye-free color contrast.
 
The system uses a handheld reflectance confocal and multiphoton microscope that contacts skin [REDACTED] [REDACTED], [REDACTED] [REDACTED], without damaging the tissue. [REDACTED]

Duration of subject participation	Single visit with a 7-day (\pm 3 days) follow-up phone call to assess for adverse events.
-----------------------------------	--

4 Introduction

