8.2 Primary Endpoints (Safety and Effectiveness)

- 100% agreement and validation of specific tissue features on VIO images (epidermis, dermis, collagen, blood vessels and pigment) in comparison to gold standard pathology images in Comparative Reader assessment.
- >90% agreement between Blinded Reader VIO image assessment and answer key developed from validation assessment.
- Safety will be assessed as the incidence of all adverse events (analyzed by severity, seriousness, and relationship to the device and procedure) that occur through the 7-day follow-up period.

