12.8 Study Exit

After the 7-day (+/-3 days) follow-up, the subject's participation in the study is complete and the Investigator or designee(s) will complete the study exit CRF.

If an adverse event occurs the subject will be followed by the Investigator until the AE is resolved or for a minimum of 30 days after the subject's participation in the study is complete.

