14.2 Reporting of Adverse Events

14.2.1 Assessments and documentation of adverse events

The Investigator or designee must collect all AEs for each subject from the time of the start of device procedure preparation to 7 days (\pm 3 days) following the end of subject study participation, whether or not deemed related to the investigational device or procedure. All AE data will be recorded on the CRF. All AEs will be followed until the event has subsided or, for a minimum of 30-days after subjects' participation has ended.

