14.4 Potential Risks to Study Subjects

The following are the possible risks associated with the VIO procedure:

- Irritation from adhesive targeting guide
- Allergic reaction such as irritation or sensitivity to immersion fluid or cover
- Pain due to pressure from the wand and/or sensitivity of the lesion
- Infection caused due to improper cleaning of the device

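### The single follow-up call may fall on any day from 4 to 10, so the primary safety endpoint has either unobserved days or no common observation period

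*Combined protocol and SAP*

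**What the plan says.** The primary safety endpoint in section 8.2, repeated in the study summary, is the incidence of all adverse events (AEs) "that occur through the 7-day follow-up period".

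The study summary describes one visit and one telephone call. The schedule in 12.1 makes that call both the AE assessment and the study exit, and lists no later contact. Section 12.7 gives the timing: "A phone call follow-up evaluation will be conducted 7 days (+/-3 days) after the study procedure to record adverse events". Section 12.8 closes the subject at that point: "After the 7-day (+/-3 days) follow-up, the subject's participation in the study is complete".

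Two other provisions bear on the point:

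- Under 12.8 and 14.2.1, an AE is followed until it resolves or for at least 30 days after participation. This applies to an AE already identified.
- Section 14.2.1 runs AE collection from device preparation to 7 (±3) days "following the end of subject study participation, whether or not deemed related to the investigational device or procedure". That is later than the end of collection implied by 8.2, 12.7 and 12.8.

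Section 13.3 places every subject with attempted imaging in the Safety Analysis Set and reports AEs for that set. It states no minimum follow-up, no cut-off day for AE onset and no rule for a call made before day 7.

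**The concern.** A follow-up call looks back. It can record only what has happened by the day it is made. The window is symmetric about day 7, so a call on day 4 complies fully with the protocol, and the subject then exits. Nothing scheduled afterwards would reveal an event that began on days 5 to 7, although those days belong to the endpoint if the 7-day period is taken at face value.

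Demonstrating safety is part of the first study objective, and the endpoint covers all AEs, whether or not related to the device. The risks listed in 14.4 include adhesive irritation, infection and "Allergic reaction such as irritation or sensitivity to immersion fluid or cover". The documents give no onset times for these, so they offer no ground for assuming that all would be evident by day 4. Few events are likely among at most 65 subjects, so one or two missed events would visibly change the reported incidence.

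**Working it through.** The plan attaches no sample size, power or threshold to the safety endpoint, so there is no figure of its own to reproduce. The check is day arithmetic.

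**Inputs.** Call at 7 ± 3 days (12.7); one contact after the procedure (study summary, 12.1); exit at the call (12.8); endpoint through the 7-day period (8.2); at most 65 subjects (study summary). The procedure day is day 0.

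**Window.** Earliest call 7 − 3 = day 4; latest 7 + 3 = day 10.

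**Reading A: the endpoint period is seven days.** Unobserved endpoint days = max(0, 7 − call day).

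| Call day | Unobserved days of 7 | Share | Days beyond day 7 |
|---|---|---|---|
| 4 | 3 | 43% | 0 |
| 5 | 2 | 29% | 0 |
| 6 | 1 | 14% | 0 |
| 7 | 0 | 0% | 0 |
| 8 | 0 | 0% | 1 |
| 9 | 0 | 0% | 2 |
| 10 | 0 | 0% | 3 |

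Assume that calls are spread evenly over the seven permitted days:

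- Calls before day 7: 3/7 = 43%.
- Mean unobserved time: (3 + 2 + 1)/7 = 0.86 day, or 0.86/7 = 12% of the period.
- At 65 subjects: 65 × 7 = 455 subject-days, of which 455 × 6/49 = about 56 are unobserved.

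If every call were on day 4, which is compliant but extreme, the share would be 3/7 = 43%.

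**From time to events.** This step needs a further assumption. Suppose onset is even over days 1 to 7, 65 subjects are enrolled and no events are reported spontaneously after the call. Events found within the 7-day period would then be:

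| Assumed true 7-day incidence | Expected subjects with an AE | Found, calls spread evenly | Found, all calls on day 4 |
|---|---|---|---|
| 2% | 1.3 | 1.14 | 0.74 |
| 5% | 3.25 | 2.85 | 1.86 |
| 10% | 6.5 | 5.70 | 3.71 |

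If onset clusters on the procedure day, when AEs are also assessed (12.1), the loss is smaller.

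**Reading B: the period ends at the call.** No event is missed by definition, but observation runs from 4 to 10 days, a ratio of 10/4 = 2.5. Under the even spread the mean is (4 + 5 + 6 + 7 + 8 + 9 + 10)/7 = 7 days. The average is as intended, but the period differs from subject to subject.

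**Does 14.2.1 close the gap?** Read literally, a day-4 exit would extend collection to 4 + 4 = day 8 at the earliest and 4 + 10 = day 14 at the latest. Days 5 to 7 are then covered on paper, but no contact is scheduled to collect anything in that time.

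**The case against.** The strongest case on the other side is that the endpoint is not clearly fixed at calendar day 7. The study summary and 12.8 describe the follow-up itself as 7 (±3) days, so the period may naturally end at the call, and then nothing is missed. This stands as a possible reading, but it only replaces unobserved days with unequal observation times.

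A second argument is that 14.2.1 already requires collection beyond exit. It does so in words only, and it conflicts with 8.2, 12.7 and 12.8.

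A third is that little depends on the matter: imaging takes place at a single visit, the protocol rates the risk as no more than minimal, and the safety endpoint has no threshold, hypothesis or comparator. This stands, and it limits the size of the point.

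A reader might also draw stronger conclusions that the documents do not support:

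- **The incidence is certain to be biased downward.** No section cuts AE counting at day 7. If everything up to the call is counted, late calls add days as early calls lose them, and the two offset under an even spread and a constant hazard. A net downward bias would need predominantly early calls or a day-7 cut-off, and the plan states neither.
- **A subject who exits on day 4 is counted as event-free for seven days.** No section says so. Section 13.3 is silent on how unequal follow-up is handled.
- **Sites that call early will look safer.** No comparison between sites is planned, and site is not among the subgroups of interest in 13.2.1.
- **12% or 43% of events would be lost.** These are shares of subject-time, and equal shares of events only if onset is uniform.

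**Conclusion.** The point holds as a weakness in how the primary safety endpoint is ascertained. The one scheduled contact may fall three days before or three days after the nominal end of the period. Depending on how 8.2 is read, the result is up to 3 of 7 endpoint days without active ascertainment, or observation of 4 to 10 days with no common time base. Section 14.2.1 cures neither.

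The unobserved share of 7-day subject-time is 12% if calls are spread evenly and 43% if all are on day 4. Both are illustrations, since the actual call days cannot be known from the plan. The effect on the number of AEs is probably modest, and its direction is not settled by the documents. It is worth correcting because the correction is cheap and works under either reading.

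**What to change.** 1. In the study summary, 12.7 and 12.8, make the data-collection window for the call one-sided: day 7 to day 10, with the present upper limit kept.
2. In 8.2 and 13.3, state that the primary safety endpoint counts AEs with onset through day 7, and that later ones are listed separately. Confirm that the CRF records the onset date of each AE. It may already do so, as 14.2.1 sends all AE data to the CRF, but the form is not in the public documents.
3. Reconcile the collection window in 14.2.1 with 8.2, 12.7 and 12.8, so that one end of collection applies throughout.

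For every completed call, unobserved endpoint days then fall from as many as 3 to 0, and all subjects share a 7-day period. Calls that are never completed remain a separate loss.

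The cost is protocol wording, a CRF check and a calling window that narrows from 7 days to 4, which is a small scheduling burden for sites. No contact is added and the latest call day is unchanged. Stating a cut-off and reporting each subject's observation time would be cheaper still and would make the unequal follow-up visible, but it would not recover the days missed by an early call.

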12.8 Study Exit

After the 7-day (+/-3 days) follow-up, the subject's participation in the study is complete and the Investigator or designee(s) will complete the study exit CRF.

If an adverse event occurs the subject will be followed by the Investigator until the AE is resolved or for a minimum of 30 days after the subject's participation in the study is complete.

12.9 Early Withdrawal of Subjects

Subjects may be withdrawn from the study at any time for the following reasons:

- o Any reason that, in the opinion of the Investigator, poses a safety hazard to the subject
- o Failure of subject to adhere to protocol requirements, including but not limited to:
 - Inability to stay awake in order to follow instructions
 - Inability to stay still for high quality images
 - Inability to follow the Investigator's or designee's instructions
- o Subject or LAR withdraws consent
- o Device non-operational at the scheduled imaging time

13 Statistical Analysis Plan

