13.3 Subject Population(s) for Analysis

Analysis populations will differ based on the purpose of the analysis. The Safety Analysis Set will include all subjects for whom an attempt was made to image lesions using the VIO device. Adverse events, protocol deviations (PDs), device malfunctions and study disposition will be reported for this set. The Full Imaging data set will include all subjects in the safety set and all VIO images. The Primary Analysis Set will include only subjects with at least 4 images of sufficient quality to be included in the training or validation set, and only images of sufficient quality to be included in these sets. The Primary Analysis Set will be used for all other descriptive summaries and for analyses of accuracy and agreement. A comparison between the Full Imaging Set and the Primary Analysis Set will be used to summarize the rate of high-quality images.

14 Safety and Adverse Events

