16.2 Recording and Addressing Device Malfunction

Throughout the study, the Investigator and study staff will report and document all device malfunctions related to the identity, quality, durability, reliability, safety, or performance of the device.

17 Study Monitoring, Auditing, and Inspecting

Representatives of the Sponsor will visit all study sites to perform monitoring and data management functions, and provide participating sites with relevant contact information, as necessary.

18 Ethical and Legal Considerations

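### A subject whose device is found non-operational before any imaging attempt can be missing from the malfunction and disposition summaries and from every analysis set

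*Combined protocol and SAP*

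**What the plan says.** All references are to the combined protocol and SAP.

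- **12.3 (Informed consent process)** makes an eligible patient a study subject once consent is signed, which is before any imaging.
- **12.9 (Early Withdrawal of Subjects)** opens with "Subjects may be withdrawn from the study at any time for the following reasons", and its last listed reason is "Device non-operational at the scheduled imaging time".
- **13.3 (Subject Population(s) for Analysis)** defines the first set: "The Safety Analysis Set will include all subjects for whom an attempt was made to image lesions using the VIO device". It then says: "Adverse events, protocol deviations (PDs), device malfunctions and study disposition will be reported for this set".
- **13.3** builds the next set on that one: "The Full Imaging data set will include all subjects in the safety set and all VIO images". The Primary Analysis Set is narrower, since it needs at least 4 images of sufficient quality. The rate of high-quality images is a comparison of these two sets.
- **12.4 (Screening)** gives every eligible, consented subject a screening number, but adds: "Only subjects who undergo device use will count towards the study's sample size".
- **16.2 (Recording and Addressing Device Malfunction)** requires that, throughout the study, "the Investigator and study staff will report and document all device malfunctions". It is not tied to any analysis set.
- **12.1 (Study Schedule)** lists an assessment of device deficiencies on the procedure day.

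The documents do not define what counts as an attempt to image.

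**The concern.** A disposition table should account for everyone who became a study subject, and a malfunction summary should cover every occasion on which the device was meant to be used. Here both begin after a step that can depend on the device itself. 12.9 creates a withdrawal reason, and on the ordinary meaning of an attempt, the disposition table in 13.3 would not show subjects withdrawn for that reason before imaging began.

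The first study objective in 8.1 includes the device's effectiveness in obtaining images in living skin. The malfunction, disposition and image-quality summaries are the planned outputs that bear most directly on whether images could be obtained at all. If subjects are lost from them in this way, the error runs in one direction, towards the device. In a study of 50 to 65 subjects, a handful of omitted cases would be visible in a percentage.

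**Working it through.** **No plan figure to reproduce.** The documents state no malfunction rate, target or denominator. The check is therefore one of set membership, followed by an illustration of scale.

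**Step 1: trace two subjects through the rules.** Both are eligible and have signed consent, so both are study subjects under 12.3.

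| Place in the plan | A: device found non-operational, nothing attempted | B: imaging attempted, device fails, no usable image |
|---|---|---|
| Study subject (12.3) | Yes | Yes |
| Event documented (16.2), if a malfunction | Yes | Yes |
| Safety Analysis Set (13.3) | No | Yes |
| Full Imaging set (13.3) | No | Yes |
| Primary Analysis Set (13.3) | No | No |
| Malfunction and disposition summaries (13.3) | No | Yes |
| Counts toward sample size (12.4) | No | Yes, if the attempt involved device use |

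Subject A is in no analysis set and in no planned summary. Subject B is kept where it matters. The gap is therefore confined to failures discovered before an attempt.

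**Step 2: check whether another set recovers subject A.** The Full Imaging set starts from the subjects in the safety set, and the Primary Analysis Set is a subset defined by image count and quality. Neither can bring back someone outside the safety set. No named set covers all consented subjects.

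**Step 3: illustrate the scale.** Inputs:

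- n = 50 imaged subjects (minimum enrolment, Appendix C) or n = 65 (maximum enrolment, 10.1).
- k = number of subjects like A. The documents give no value, so k = 1, 3 and 5 are assumptions.
- No malfunction in any attempted session, also an assumption.

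Rate with subjects A left out = 0/n. Rate with them counted = k/(n + k). This takes each of the k as a malfunction under 16.1. Intervals are exact (Clopper-Pearson) 95%.

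| | n = 50 | n = 65 |
|---|---|---|
| Left out | 0/50 = 0% (0 to 7.1%) | 0/65 = 0% (0 to 5.5%) |
| k = 1 counted | 1/51 = 2.0% (0.0 to 10.4%) | 1/66 = 1.5% (0.0 to 8.2%) |
| k = 3 counted | 3/53 = 5.7% (1.2 to 15.7%) | 3/68 = 4.4% (0.9 to 12.4%) |
| k = 5 counted | 5/55 = 9.1% (3.0 to 20.0%) | 5/70 = 7.1% (2.4 to 15.9%) |

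At k = 5 the full-count rate lies above the upper limit that would be reported with those subjects left out (9.1% against 7.1%, and 7.1% against 5.5%). At k = 1 or 3 it lies inside. The table shows sensitivity to k and is not a forecast.

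**Step 4: check the endpoints.** The two effectiveness endpoints in 8.2 are agreement measures on images already acquired. A subject with no image contributes nothing to either, so neither figure changes.

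**The case against.** The strongest reply is that exclusion is a possible reading and not a rule. 12.9 is permissive and does not place the withdrawal before an attempt. Since an attempt is undefined, preparing the subject and trying to start a device that does not respond could be counted as one, and that subject would then be in the Safety Analysis Set. This stands. It makes the loss a risk that depends on each site's judgement, which is itself a reason to define the term.

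Second, the events are not hidden. 16.2 documents every malfunction, 12.1 schedules a deficiency assessment, and 14.2.2 sends relevant malfunctions to the IRB and authorities. Nor does 13.3 forbid wider reporting, and parts of the later sections are redacted. This also stands as far as recording goes. But 13.3 is where the reporting population is set, and the population it names requires an attempt.

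Third, no malfunction rate is an endpoint, and 12.4 is only a counting rule that excludes no one from reporting. Both are correct. They limit the point to descriptive summaries.

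Fourth, not every non-operational device is a malfunction. 16.1 separates malfunction from misuse, and 6.1.7 describes a full-storage state in which no further images can be collected. This stands and shapes the fix.

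A reader might infer more: that the plan removes the device's complete failures from the results, or that every reported set is conditional on a working device. The documents do not support that. The safety set is conditional on an attempt and not on success, so a session that is attempted and yields nothing stays in.

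**Conclusion.** The point holds in a limited form. The summaries in 13.3 start from an imaging attempt, while 12.9 allows a study subject to leave because the device was not working. A failure found before any attempt can therefore go unreported in the analysis even though it was documented. Any resulting bias favours the device and affects the malfunction and disposition summaries, and through the shared denominator the image-quality summary. It does not touch the reader-agreement endpoints.

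The size is unknown. The range of 2.0% to 9.1% (1.5% to 7.1% with 65 imaged) rests on assumed counts of 1 to 5, on no other malfunction having occurred, and on a per-subject rate that the plan does not itself define. The conclusion also rests on the ordinary meaning of an attempt. If a failed start-up were expressly counted as one, such cases would be retained and the gap would shrink to subjects for whom nothing at all was tried.

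**What to change.** In 13.3:

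1. Report study disposition and device malfunctions for all consented, eligible subjects, using the definition in 12.3. The screening numbers assigned under 12.4 should supply the denominator.
2. Give withdrawal because the device was non-operational its own row, and classify each case as malfunction or misuse under 16.1. Cases that are neither, such as full storage, should be stated as such. Do not count every such withdrawal as a device failure automatically.
3. Define an attempt to image.
4. Keep the Safety Analysis Set for adverse events.

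In 12.8, state that the exit form is completed for early withdrawals. At present it is described only after the 7-day follow-up, and 12.9 specifies no data capture.

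**Cost.** This is a wording change plus one form for each early withdrawal. It needs no extra subjects or imaging, and the accuracy analyses are unchanged. The drawback for the sponsor is that the malfunction and disposition figures may look slightly less favourable.
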